2.3. Research Center Information

Name of research center	Address
Ankara Bilkent City Hospital	[name]
	[name]

Note: No service is received from outside the center regarding the research.

3. General Summary of the Clinical Trial

Background	Eye diseases stand out as a major public health problem worldwide and constitute one of the
	leading causes of vision loss. Diseases such as diabetic retinopathy, glaucoma and macular
	degeneration are among the problems that can seriously affect the quality of life and lead to
	vision loss. Therefore, early diagnosis of these diseases is vital for determining effective
	treatment methods and protecting and improving the quality of life of patients.
	In recent years, artificial intelligence (AI) technologies in the field of medicine have offered
	great potential in disease diagnosis and management. Artificial intelligence algorithms,
	especially those used for retinal image analysis, play an important role in the early diagnosis of
	eye diseases and the determination of treatment methods. The use of artificial intelligence in
	the field of ophthalmological clinical research is mostly related to the prediction and diagnosis,
	treatment and interventions, and prevention and management of ophthalmic diseases. In this
	context, ophthalmic imaging and early screening systems supported by artificial intelligence
	technology play an effective role in the diagnosis of diseases such as diabetic retinopathy,
	glaucoma and macular degeneration.
	Diabetes is a major global health problem with an estimated 463 million people living with
	diabetes worldwide. This number is expected to increase to 700 million by 2045 [1]. Diabetic
	retinopathy (DR), a common complication of diabetes, is considered the leading cause of new-
	onset blindness among adults aged 20–74 years [2]. As the prevalence of diabetes continues to
	increase, the global DR patient population is projected to increase to 160 million by 2045 [1].
	Early diagnosis and timely treatment of DR can reduce 95% of blindness from this cause [3].
	Therefore, DR screening programs are recommended for patients with diabetes by the World
	Health Organization [4].
	Glaucoma is characterized by optic disc cupping and visual field distortion, and is the most
	common cause of irreversible blindness, affecting more than 70 million people worldwide [5,7].

Document No	TF.01.CIP.01
Issue Date	01.05.2023
Revision No	V.00
Revision Date	:=:

	The number of patients with glaucoma is expected to increase due to population growth and aging worldwide; it is projected to reach 112 million by 2040 [6]. Most vision loss from glaucoma can be prevented with early diagnosis and timely treatment [8]. However, glaucoma is diagnosed by a glaucoma specialist via ophthalmoscopy or fundus images [9,10]. Such manual optic disc assessment is time-consuming and labor-intensive, and is not applicable to large populations. Therefore, improvements in glaucoma screening methods are needed. Artificial intelligence may pave the way for cost-effective glaucoma screening programs, such as automatic detection of glaucoma from fundus images. Macular degeneration, a disease affecting the macula region of the retina, usually causes progressive vision loss [11]. Age is the strongest risk factor for macular degeneration, with almost all cases occurring in people over the age of 60 [11]. With the aging population, macular degeneration will continue to be a major cause of visual impairment worldwide. The number of patients with macular degeneration is projected to reach 288 million by 2040 [12]. This is an important indicator of the global burden of macular degeneration. Consequently, screening patients with macular degeneration and providing appropriate medical interventions in a timely manner can reduce vision loss and improve patients' vision [13]. Al has the potential to facilitate automatic detection of macular degeneration and prediction of disease progression.
Study Rationale	Diabetes is a chronic disease that affects millions of people worldwide. As the prevalence of diabetes increases, the incidence of eye diseases such as diabetic retinopathy (DR), glaucoma and macular degeneration also increases. An estimated 93 million people worldwide are known to have diabetic retinopathy, and approximately 28 million of these people have severe forms that threaten their vision [14]. Glaucoma has become one of the leading causes of vision loss, affecting 76 million people worldwide, and this number is expected to increase to 111.8 million by 2040 [15]. Macular degeneration affects 196 million people worldwide, and this number is predicted to reach 288 million by 2040 [16]. Early diagnosis of these diseases is of great importance to preserve the quality of life of patients.
	A similar situation is observed in Turkey. As the prevalence of diabetes increases, eye problems related to this disease are also seen more frequently. According to studies conducted in Turkey, diabetic retinopathy rates range from 15% to 45% [17]. Glaucoma and macular degeneration are other serious eye diseases that are especially common among the elderly population. The prevalence of age-related macular degeneration in Turkey varies between 2% and 8% [18]. Early diagnosis and regular screening are critical to preventing vision loss. However, as is the case worldwide, the number of patients in Turkey who have regular eye screenings for diabetic retinopathy, glaucoma and macular degeneration is not at the desired level. Therefore, technological solutions for the early detection of these diseases are becoming increasingly important.
	The Retinow AI device is an image interpretation device that automatically performs diabetic retinopathy, glaucoma and macular degeneration screenings. It aims to increase access to screening for these diseases by healthcare providers and to reduce screening costs. This clinical study was designed to evaluate the sensitivity and specificity of the Retinow AI device in screening these three important eye diseases.
Research device	Cloud-Based Retinow Al Software for Diagnosing Retinal Disorders
Number of	915
Participants	
	I

Revision Date	920
Revision No	V.00
Issue Date	01.05.2023
Document No	TF.01.CIP.01

Inclusion	Patients with diabetic retinopathy, glaucoma or macular degeneration
criteria	Volunteers with written informed consent form
criteria	Volunteer must be 18 years or older
	Healthy individuals without retinal disorders
	Treating marviduals without retinar alsoraers
Exclusion	Volunteers who do not want to have fundus imaging
criteria	Cases that do not comply with fundus photography for any reason
	Patients with conjunctival and corneal infections,
	People with hereditary or congenital retinal diseases,
	People with cataracts,
	People with uveitis,
	Patients with permanent visual impairment in one or both eyes,
	Patients with correction of + 6D and above – 6D,
	Pregnant patients.
Study	
	To demonstrate the sensitivity and specificity of the automatic image analysis of the Retinow
objectives	Al device in order to screen diabetic retinopathy, glaucoma, macular degeneration and healthy
	individuals with no pathological findings in their retinas who come to the retina and glaucoma
	unit for these diseases.
Endpoints	Analysis of sensitivity, specificity and accuracy of the Retinow Al device.
**	
Planned	01.06.2023-01.10.2023
duration of	
clinical trial	
S.II.IIOGI CITGI	

4. Identification of Research Device

4.1. Summary Description of The Investigational Device

Retinow Al is a software, a medical device that aims to solve a global problem that eliminates the risk of vision loss, especially in developed countries. Retinow Al provides rapid screening and triage without the need for a trained expert to evaluate digital retina (fundus) images. Digital retina images pass through the Retinow Al cloud system and are interpreted with the help of artificial intelligence, helping to detect diabetic retinopathy, glaucoma and macular degeneration diseases.

4.2. Intended Use

Retinow AI is a cloud and artificial intelligence based retinal scanning and identification system. Retinow AI is used to analyze diabetic retinopathy (DR), age-related macular degeneration (AMD) and glaucoma diseases of patients who have not previously been diagnosed with the disease, in a short time, through fundus images, thanks to artificial intelligence. Retinow AI presents a report to the user through the system without the need for any expert opinion. It works as a decision support mechanism for specialist or non-specialist physicians. It detects pathological areas in the retina and automatically detects problems.

Document No	TF.01.CIP.01
Issue Date	01.05.2023
Revision No	V.00
Revision Date	:=:

4.3. Clinical Device Traceability

To ensure traceability during the clinical trial, only one version of the Retinow AI software (software number RAI01-V01.0.1) will be used. No changes will be made to the software version during the clinical trial.

4.4. Use of Device for Research Purposes

Retinow Al is designed for use by healthcare providers. The user must have sufficient understanding of the language in which the user manual was prepared. Researchers who will conduct the study will be sufficiently informed about the device with the help of the user manual before the study starts. The IFU document and researcher brochure will be provided to researchers to access the instructions for use of the Retinow Al software to be used for research purposes before the clinical study. (See TF.01.IFU.01, TF.01.IBF.01)

4.5. Indications

Retinow Al software is used in the diagnosis of diabetic retinopathy, glaucoma and macular degeneration diseases.

4.6. Contraindications

Contraindications for Retinow Al software are listed below;

- o Patients with conjunctival and corneal infections,
- o People with hereditary or congenital retinal diseases,
- o People with cataracts,
- o People with uveitis,
- o Patients with permanent visual impairment in one or both eyes,
- o Patients with correction of + 6D and above 6D,
- o Pregnant patients.

4.7. Target User Groups

Retinow Al is designed for use by healthcare providers. The user must have sufficient understanding of the language in which the user manual was prepared.

4.8. Target Patient Population and Research Population

There is no restriction on the gender and physical structure of the patient where our device will be used. Our device should be used for 3 identified diseases: Macular degeneration, diabetic retinopathy and glaucoma. Retinow Al software should be used on patients who are 18 years old or older. The target patient population and study population were persons aged eighteen years and over who presented to an ophthalmologist for an eye examination to detect diabetic retinopathy, macular degeneration, and glaucoma.

4.9. Side Effects and Risks

The device does not have any undesirable side effects.

Revision Date	32%
Revision No	V.00
Issue Date	01.05.2023
Document No	TF.01.CIP.01

4.12. Working Principle of the Device

The working principle of the Retinow AI system is as follows.

- The user logs in to retinow.com.tr.
- The user login on the site enters the system with the license given by Retinow Al.
- Through the cloud system in Retinow AI, the user uploads patient information and fundus images of the patient to the system.
- Retinow Al analyzes the uploaded fundus images and presents them to the user in the form of a detailed report.
- The user can follow up the patient from the system. Can examine images in detail and keep records.

4.14. Clinical Study Device Information

Device Name	Device Brand	Device Model
Cloud-based software Retinow AI for diagnosis of retinal disorders	Retinow	RAI01

Product Code - Referance No: RAI01-V01

Document No	TF.01.CIP.01
Issue Date	01.05.2023
Revision No	V.00
Revision Date	920

Document No	TF.01.CIP.01
Issue Date	01.05.2023
Revision No	V.00
Revision Date	920

Document No	TF.01.CIP.01	
Issue Date	01.05.2023	
Revision No	V.00	
Revision Date	:=:	

7. Objectives and Hypotheses of Clinical Research

The main purpose of this clinical study is to evaluate the effectiveness and reliability of Retinow Al software in the diagnosis of common eye diseases such as diabetic retinopathy, glaucoma and macular degeneration. Retinow Al is a cloud-based artificial intelligence software that aims to detect diabetic retinopathy, glaucoma and macular degeneration diseases through fundus photographs. The software stands out with its ability to detect disease symptoms at an early stage and accelerate the diagnosis process. In addition, it is claimed that this software, which has reached a 90% accuracy rate during pre-clinical validation studies, can achieve similar results to the diagnostic accuracy of specialist physicians. This study examines the usability of Retinow Al software by both specialist and non-specialist physicians and its potential to save time in diagnostic processes. It is anticipated that the software can improve patient management, reduce costs and increase the efficiency of general healthcare services by accelerating the diagnosis of eye diseases. Certain eligibility criteria have been defined for the subjects and users to be examined within the scope of the study.

Retinow Al is designed for use by healthcare providers. The user must have sufficient understanding of the language in which the user manual was prepared.

Primary Objective:

The primary objective is to evaluate the capability of Retinow AI software to diagnose diabetic retinopathy, glaucoma, and macular degeneration diseases with high accuracy from fundus photographs. The performance of the software will be compared with the diagnoses made by expert physicians and the accuracy, sensitivity, and specificity metrics will be measured. The hypothesis that Retinow AI can reach 90% accuracy will be tested. In this context, the capability of Retinow AI to consistently identify the same disease symptoms in different fundus images will be evaluated by analyzing false positive and false negative results.

Primary Hypothesis:

It is hypothesized that Retinow AI software can diagnose eye diseases such as diabetic retinopathy, glaucoma, and macular degeneration at an early stage with 90% accuracy from fundus photographs. It is anticipated that the software will be able to achieve sensitivity and specificity rates similar to those of expert physicians in the diagnosis of these diseases.

8. Design of Clinical Trial

This clinical trial was designed based on the evaluation of preclinical studies conducted. This clinical trial is a single-center, observational, prospective and cross-sectional study planned to be conducted at Ankara Bilkent City Hospital to determine the primary endpoints of sensitivity, specificity and accuracy of the Retinow Al device for diabetic retinopathy, glaucoma and macular degeneration diseases.

The clinical trial, clinical trial plan, clinical trial results report will be conducted in accordance with the ethical principles of the Declaration of Helsinki, SS-EN ISO 14155:2020 principles and current national and international regulations governing this clinical trial. A signed Declaration of Helsinki will be obtained from all participants in the clinical trial.

Healthy participants who do not have Diabetic Retinopathy, glaucoma, macular degeneration diseases or any eye disease (no pathological findings in the retina) will be included in the study. Inclusion and exclusion criteria of the participants are specified in section 9.

Methods and tools to be used in the study:

• A non-mydriatic fundus camera will be used to diagnose diabetic retinopathy, glaucoma and macular degeneration, to analyze the retina of healthy individuals and to enable specialist physicians to diagnose diseases from fundus images. This camera allows detailed visualization of the vessels and retinal structure at the bottom of the eye by taking high-resolution retinal photographs. The cleaning of optical components will be

Document No	TF.01.CIP.01
Issue Date	01.05.2023
Revision No	V.00
Revision Date	N=1

done regularly by hospital staff.

• Retinow AI software: Retinow software will be used by retina specialists to evaluate fundus images and compare results for clinical validation of the Retinow AI device. Retinow AI is an artificial intelligence-based software that diagnoses eye diseases by analyzing fundus images. The computer systems on which the software runs will be checked regularly, virus scans and security updates will be made. The analysis results of the software will be compared periodically with the results of specialist ophthalmologists. Since the latest version of the Retinow AI software will be used, no changes will be made to the software during the clinical study.

The clinical study protocol will be carried out in the following steps:

- 1. Participant Selection: Participants who apply to the retina and glaucoma clinic and meet the study inclusion and exclusion criteria will be determined by the specialist physicians in the study.
- 2. Information and Consent: Participants who meet the eligibility criteria will be provided with detailed information about the study and written informed consent will be obtained from them. The content of the informed consent form is arranged in accordance with the relevant integrity and data protection legislation. In the volunteer information and the informed consent form, the volunteer will be fully informed about how the clinical trial data will be collected, used and published.
- 3. Imaging Directions: Participants will be directed to the fundus imaging room by a specialist doctor for fundus photography. Retinal patients diagnosed with diabetic retinopathy, glaucoma, and macular degeneration will be sent for color fundus photography after the initial diagnosis examination. Similarly, healthy participants with no pathological findings in their retinas will be sent for a control fundus photography.
- 4. Fundus Photography: In this study, no invasive procedure will be applied to the patient, and the retinal photography will be taken by the camera operator with a special non-mydriatic digital camera called a fundus camera. In some patients diagnosed with Retinow AI, pharmacological dilatation (mydriasis) using a dilatation solution may be required to obtain a fundus image of sufficient quality. The dilatation procedure will be performed only by healthcare personnel (general practitioners, nurses, etc.) who are competent and trained in this regard.
- 5. Recording of Images: Right and left fundus images of each participant will be taken and these images will be recorded by the responsible researcher. The principal investigator will download the images via the hospital's PACS system.
- 6. Analysis of Images: Fundus photographs will be analyzed by the Retinow AI device. Then, they will be analyzed by expert ophthalmologists for gold standard evaluation.

Revision Date	920	
Revision No	01.05.2023 V.00	
Issue Date		
Document No	TF.01.CIP.01	

8. Gold Standard Assessment: The gold standard assessment results performed by specialist doctors will be used to determine the sensitivity and specificity of the Retinow Al device.

Al Analysis: Retinow Al software will analyze the collected images within 24 hours of image acquisition. This rapid analysis will allow for a near real-time comparison with expert diagnoses.

Clinical data will be fed into Retinow Al software and the success metrics (Accuracy, Sensitivity, Specifity) will be evaluated. Diagnostic labels provided by Retinow Al software will be compared with labels provided by expert ophthalmologists. Performance metrics of accuracy, sensitivity and specificity will be calculated.

The clinical study will be completed when the predicted number of data is reached

9. Subjects

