ANNEX 1.

STATISTICAL ANALYSIS PLAN

Analysis Population and Procedures

Analyses will be performed on a Per Protocol (PP) basis only. The PP analysis will include participants who completed the study per protocol and this population will accurately reflect the effectiveness and reliability of the software in diagnosing diabetic retinopathy, glaucoma and macular degeneration.

Baseline Data and Endpoints Descriptive Statistics

Baseline Data:

Baseline data includes the age and gender information of all patients participating in the clinical study. This data does not affect the results of the Retinow AI software. It will only be collected to obtain information about the age and gender distribution.

Endpoints Descriptive Statistics:

Endpoints are the sensitivity, specificity and accuracy rates of the Retinow Al software in diagnosing diabetic retinopathy, glaucoma and macular degeneration diseases. These rates show how well the software agrees with the diagnoses made by specialist physicians. Descriptive statistics are used to measure these rates. The definitions of these rates are provided below.

Sensitivity: The ability of the software to correctly identify individuals with the disease. High sensitivity reduces the probability that the software will miss signs of the disease. (True positive rate).

Specificity: The ability of the software to correctly identify healthy individuals. High specificity minimizes false positive results. (True negative rate).

Accuracy: It is defined as the percentage of correct results in all diagnoses of the software.

These descriptive statistics will be used to further evaluate the reliability, effectiveness, and usability of the Retinow Al software in clinical applications.

Analytical Procedures

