The comparisons of the diagnosis of disease results in the clinical trial by the doctor and the Retinow Al software will be examined. The results will be analyzed with Cohen's Kappa analysis. The parameters to be analyzed are sensitivity, specificity and accuracy values. Sensitivity is defined as the accuracy between positive findings according to the clinical reference standard; It will be calculated as the ratio of eyes with positive findings according to the reference standard and positive results with the Retinow Al system. Specificity is defined as the accuracy between negative findings according to the clinical reference standard; It will be calculated as the ratio of eyes with negative findings according to the reference standard and negative results with the Retinow Al system. (Positive findings indicate being sick, negative findings indicate being healthy)

Statistical analyses will be performed using the Python programming language version 3.11.4 and the TensorFlow library version 2.10.0. In addition to these calculations, the Cohen's Kappa method will also be used for the analysis of the results. These analyses involve the use of the specified software versions and tools in the data processing and model building stages. This process aims to specify the relevant software and versions to ensure the reliability and framework of the research results. Considering the referenced cases as 'positive' and the non-referenced cases as 'negative', the sensitivity, specificity and accuracy scores are clinically significant measurements and will be calculated with 95% confidence intervals. For each disease, tables will be created to compare the sensitivity and specificity of the algorithm with the reference standard. The reference standard is defined as the majority decisions of the ratings of 3 expert ophthalmologists. The definitions of the positive and negative cases to be analyzed are given below.

Document No	TF.01.CIP.01
Issue Date	01.05.2023
Revision No	V.00
Revision Date	120

		Retinow AI				
		Disease	No Disease	Total	Kappa	p
Doctor	Disease	TP	FN			
	No Disease	FP	TN			
	Total					

Kappa Score: Cohen's Kappa score is a statistical method used to measure the agreement between two raters or observers. It shows how much the two parties agree, taking into account the probability of random agreement.

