P: It is used in statistical tests to determine whether the results are significant. In a hypothesis test, it shows how much the data deviates from the expected distribution and expresses the probability that the results occurred randomly.

True Positive (TP): This refers to the situation where the software correctly diagnoses the disease. That is, it occurs when the software classifies an actual disease as a patient.

True Negative (TN): This refers to the situation where the software does not correctly diagnose the disease. That is, it occurs when the software classifies an actual healthy state as healthy.

False Positive (FP): This refers to the situation where the software incorrectly diagnoses the disease. That is, it occurs when the software classifies an actually healthy condition as sick.

False Negative (FN): This refers to the situation where the software does not incorrectly diagnose the disease. So it happens when the software classifies a real disease as healthy.

These terms are used to evaluate the accuracy and precision of software in classifying a disease or condition. True Positive and True Negative results represent conditions that were correctly diagnosed, while False Positive and False Negative results represent conditions that were misdiagnosed. Below is the calculation of sensitivity, specificity and accuracy values in our clinical study.

```
Sensitivity = TP/(TP + FN)
Specificity = TN/(TN + FP)
Accuracy = (TN + TP)/(TN + TP + FN + FP)
```

The passing criteria for the Retinow AI software in the clinical study will be based on its accuracy, sensitivity and specificity in diagnosing diabetic retinopathy, glaucoma and macular degeneration. The passing criteria were determined as 90% accuracy, 90% sensitivity and 90% specificity for all diseases. These threshold values are necessary for the software to be used as a reliable diagnostic tool in the clinical setting. In addition, it will be mandatory for the reliability of the study and the validity of the results to be kept below 10% of the possible technical errors and data loss rates. When these criteria are met, Retinow AI will be considered successful; otherwise, the software will not pass the study.

Sample Size

The required sample size for each study whose results will be analyzed with Cohen's Kappa analysis was calculated using Arifin's [82] calculation tool, which was developed based on the formula presented by Donner and Eliasziw [81].

Document No	TF.01.CIP.01

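### The Primary Hypothesis claims early-stage diagnosis, but the available plan never identifies early-stage cases, so a pass would not support that part of the claim

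*Combined protocol and SAP*

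**What the plan says.** **Hypothesis.** Section 7, Primary Hypothesis, puts the target as diagnosis "at an early stage with 90% accuracy from fundus photographs". The opening paragraph of Section 7 also credits the software with "its ability to detect disease symptoms at an early stage".

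**Objective.** The Primary Objective in the same section names no stage: the software is to "diagnose diabetic retinopathy, glaucoma, and macular degeneration diseases with high accuracy from fundus photographs", and a 90% accuracy hypothesis is to be tested.

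**Analysis.** Annex 1 (SAP) names no stage either. Sensitivity is "The ability of the software to correctly identify individuals with the disease", calculated as TP/(TP + FN). Under Analytical Procedures, "Positive findings indicate being sick, negative findings indicate being healthy". The results table for each disease has two categories, disease and no disease. The rule for success reads "The passing criteria were determined as 90% accuracy, 90% sensitivity and 90% specificity for all diseases".

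**Data and participants.** Section 9.1 admits patients with any of the three diseases, without a stage limit or quota. Section 9.2 excludes permanent visual impairment. The baseline data listed in Annex 1 are age and gender. The reference standard is the majority rating of three expert ophthalmologists, and the available text ties no grading scale to it.

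**The concern.** Early detection is not a stray phrase in this plan. The rationale in Section 3 rests on it, and Section 4.2 intends the device for people not yet diagnosed. A reader of the final report would naturally take a pass as confirming the Primary Hypothesis as written, including its early-stage part.

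A statistician who followed Annex 1 exactly would have no variable that identifies an early case. Under Section 8, step 3, patients are photographed after a diagnosis has been made in a specialist clinic, and nothing secures a given number of early cases. Sensitivity pooled over stage is an average weighted by the case mix, so good detection of advanced disease can offset weaker detection of early disease. At stake is whether the conclusion reaches further than the evidence. The calculation of the pooled figures is not in question.

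**Working it through.** **1. The plan's own figure.** Annex 1, Sample Size, plans 305 people for each of three diseases: 3 × 305 = 915, which matches the total in Section 3. The inputs behind 305 are not in the available text, so it was not re-derived and no error is claimed there.

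**2. Hypothesis against analysis.**
- Stage in the Primary Hypothesis: yes.
- Stage in the Primary Objective, endpoints, definitions of positive and negative, results table, formulas or pass rule: no.
- Stage among the eligibility criteria or listed baseline data: no.

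The mismatch lies between one statement of the hypothesis and the rest of the plan.

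**3. What a pooled 90% allows.** Let *f* be the share of early cases among the diseased, and Se_early and Se_adv the sensitivities in early and advanced disease. Then

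pooled sensitivity = *f* × Se_early + (1 − *f*) × Se_adv.

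Setting this to 0.90 gives

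Se_early = [0.90 − (1 − *f*) × Se_adv] / *f*.

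The documents give neither *f* nor Se_adv; both are assumptions, shown over a range. Example: *f* = 0.20 and Se_adv = 0.98 give (0.90 − 0.80 × 0.98)/0.20 = 0.116/0.20 = 0.58.

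| Early share *f* | Se_adv 95% | Se_adv 98% | Se_adv 100% |
|---|---|---|---|
| 20% | 70% | 58% | 50% |
| 30% | 78% | 71% | 67% |
| 50% | 85% | 82% | 80% |
| 70% | 88% | 87% | 86% |
| 90% | 89% | 89% | 89% |

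**4. Chance of meeting the sensitivity criterion for one disease.** This is exact, from the sum of two binomials. It assumes Se_adv = 98% and 305 independent diseased units, which takes all 305 participants as diseased because the diseased/healthy split is not given. Annex 1 says that the measures "will be calculated with 95% confidence intervals", but not whether the estimate or its lower limit must reach 90%, so both are shown (Clopper-Pearson for the limit).

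| *f* | Se_early | Pooled | Estimate ≥ 90% | Lower limit ≥ 90% |
|---|---|---|---|---|
| 20% | 70% | 92.4% | 96% | 27% |
| 30% | 70% | 89.6% | 40% | 0.7% |
| 50% | 80% | 89.0% | 29% | 0.5% |
| 50% | 70% | 84.0% | 0.1% | 0% |

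With 152 diseased units the chances on the estimate are 91%, 46%, 38% and 1.4%.

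**5. Limit of the arithmetic.** The hypothesis is stated in accuracy, while steps 3 and 4 concern sensitivity, one of the three pass criteria. The corresponding accuracy figure also needs the number of healthy controls and the specificity, and the documents give neither the split nor an expected specificity.

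**The case against.** **The hypothesis is also stated without stage.** The Primary Objective, endpoints, SAP definitions and pass rule agree with one another and name no stage. On that view the early-stage phrase is loose wording and the analysis is sound. This stands in part: a reader might infer that the analysis fails to test the primary hypothesis at all, and the documents do not support that. The stage-free accuracy statement is tested. What remains untested is the early-stage part of the only passage headed Primary Hypothesis.

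**Text is missing.** Some sections are not available, and the steps in Section 8 run from 6 to 8. A diabetic retinopathy severity scale appears as reference 80, but the visible text does not cite it. A staging rule elsewhere cannot be excluded. Annex 1 also has a second, undefined wording ("Considering the referenced cases as 'positive' and the non-referenced cases as 'negative") that may carry a different cut-off. This stands, so the point is limited to the available text.

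**Case mix may be favourable.** Excluding permanent visual impairment removes some advanced cases, and Section 9.4 includes suspected as well as diagnosed patients. A reader might infer that advanced disease will carry the result, or that a pass with poor early-stage sensitivity is likely. No passage says so, and the tables show that it needs early cases to be a minority. The exclusion does not make the sample early-stage, however, and without a record of stage the report could not show which situation applied.

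**Reporting.** That a pass would in fact be reported as early-stage accuracy is conjecture; Annex 1 says only that the software would be considered successful.

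**Conclusion.** The concern holds in a limited form. In the available text, the analysis can test whether the software reaches 90% on figures pooled over stage. It cannot test whether it does so in early-stage disease, so a pass would not support the early-stage part of the Primary Hypothesis.

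The size of the gap cannot be fixed from the documents. With advanced-stage sensitivity assumed between 95% and 100%, early-stage sensitivity at a pooled 90% falls short of 90% by 20 to 40 points at a 20% early share, by 5 to 10 points at a 50% share, and by about 1 point at a 90% share. A large hidden shortfall requires early cases to be a minority. It also becomes much less likely to pass if the lower confidence limit, rather than the estimate, must reach 90%. The point should be settled before results are reported; it does not call the pooled analysis into doubt.

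**What to change.** Before results are seen, choose one of two changes.

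**(a) Make the early-stage part testable.** Define early stage for each disease. Have the three expert readers already planned record it, with the same majority rule. Pre-specify two results as the evidence for the early-stage part of the hypothesis, beside the pooled figures: sensitivity in early-stage cases with a 95% confidence interval, and accuracy in early-stage cases plus healthy controls.

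The cost is three definitions, slightly longer grading and one more table. The plan mentions ratings but describes no recording form, so the way stage is recorded must be written down too. The interval for early cases will be wider. For example, at a 20% early share of 305 diseased units (61 cases) and 90% sensitivity, the approximate half-width is 1.96 × √(0.9 × 0.1/61) = 7.5 points, against 1.96 × √(0.9 × 0.1/305) = 3.4 points for all 305.

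**(b) Narrow the claim.** Remove the early-stage wording from the Primary Hypothesis and make no early-detection claim in the report. This is a change of wording only; the cost is a narrower conclusion.

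If a staging rule exists in a part of the plan not available here, a cross-reference to it from Annex 1, with the early-stage results of (a), would serve.
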